To estimate sample size needed, we first assess the ability to demonstrate the feasibility that the intervening variable, seizures, can be prevented with early treatment. In the placebo arm, we expect that all patients will develop seizures, but to be conservative we assume that 2/24 in the placebo arm do not develop a seizure within the time frame, making the proportion of seizure occurrence 0.917. In the vigabatrin arm, we assume it mirrors the proportion well controlled in our ongoing TSC project, thus our seizure rate will be estimated at 5/24 (19 remain seizure free to date) or 0.208. A Fisher's exact test with a 0.05 two-sided significance level will have 99% power to detect the difference between a Group 1 proportion,  $p_1$ , of 0.917 and a Group 2 proportion,  $p_2$ , of 0.208 when the sample size in each group is 24.

The percent difference for seizures used in the power calculation is based on data collected during our current TSC project. We note that this is a large difference. However, it is conservatively estimated through discounting our expected 100% seizure rate in the control arm to 91.7% and using our observed data for the treatment arm, which under a strict protocol could be higher. Even if the vigabatrin treatment is less effective than expected and 10/24 (0.417) in the treatment arm experience seizures, we still have greater than 90% power to detect this treatment effect.

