## **Analyses**

The primary analyses for this Phase IIb trial consists of two testing hypotheses: time to onset of a first clinical seizure, documenting that the intervening variable (i.e. vigabatrin treatment) does indeed reduce or delay clinical seizures and comparison of the developmental outcomes at 24 months. While vigabatrin is used to control seizures and thus suppress them once seizure onset has been identified, it is presumed that if given prior to occurrence of clinical seizures occurring such a delay will be observed, but this is untested. Thus, the study endpoint of time to first clinical seizure is an essential step in determining the impact on developmental ability. The first step in the analyses will include demonstrating a difference between the proportion seizure free in the treatment arm versus placebo. This will be assessed at two years of follow-up using a chi square test and an intention to treat analysis. Supportive analyses will use a time to first seizure analysis using Cox regression methods to evaluate the treatment effects. Kaplan Meier analyses will provide graphical and overall test of the incidence of seizures. Cox models with age, gender, baseline number of epileptiform discharges included with treatment group will be attempted keeping in mind the relatively small sample size. Tests will use 2 sided Type I errors of 0.05.

The next key analysis to move to a go decision for Phase III will focus on the Bayley-III. While ideally the primary assessment would be made at age 5 or 6, there will be insufficient follow-up to make such an assessment in this grant period. We will perform assessment of the Bayley-III using the standardized cognitive scores over time using the constrained longitudinal data analysis (cLDA) method proposed by Liang and Zeger

which assumes a common mean across treatment groups at Baseline and a different mean for each treatment at each of the post-Baseline time points (12, 24, and 36 months for those who have them). In this model, we use a response vector that includes the time 0 or the baseline measure and assessments at each post-baseline observation time point. Each time point is considered a categorical variable so that no overall linear restrictions are imposed on the means over time.

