EEG biomarker feasibility: The outcome measure will be the sensitivity and specificity of EEG epileptiform activity in predicting outcomes at 24 months for each treatment group. To confirm the feasibility of using EEG biomarkers to identify TSC infants at risk for developing epilepsy, sensitivity and specificity of EEG epileptiform activity at each time-point for predicting subsequent development of epilepsy by 24 months of age will be conducted within each treatment arm. Successful treatment in the vigabatrin arm should produce significantly poorer specificity and lower positive predictive value (PPV) by mitigating the predictive power of the EEG epileptiform activity. Exploratory analysis will further evaluate the timing of EEG change with time to seizure onset and type of EEG change with epilepsy type and treatment response as a covariate in the Cox proportional hazards assessment of time to clinical seizure. Additional analysis will evaluate the separate impact of TSC clinical features and concurrent AEDs. Our estimate is that 75% will develop the EEG biomarker prior to clinical seizures, some of the enrolled infants will

develop neither EEG biomarker nor seizures and some will develop seizures prior to being identified with the EEG biomarker or never develop the EEG biomarker despite the onset of clinical seizures. If the incidence of developing the EEG biomarker relative to the incidence of seizures without the EEG biomarker is very low, then the efficacy of treatment would have to be great to warrant the cost of monitoring. Thus, evaluation of this aim will be a tradeoff between biomarker incidences versus the treatment benefit. Descriptive statistics and numbers needed to treat (NNT) will be used to evaluate this endpoint.

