Additional measures and analyses considerations: We will use descriptive statistics to quantify the percentage of patients requiring unblinded treatment after randomization and the duration of blinded treatment within the study period. We will also determine the percentage of randomized patients at 24 and 36 months of age with drug-resistant epilepsy as a clinically meaningful and significant correlate to the time to first seizure measure. As noted above, Cox regression models will be attempted with the pre-treatment covariates from the baseline and index EEG (that is, the biomarker findings that initiated the randomization) to examine if there are gradients in the predictors and levels of risk/time to events that can be predicted. These analyses will be done both within the treatment group and with the interaction of treatment and biomarkers included in the model. Since subject randomization is based on EEG findings, not seizure onset and the most common age of seizure onset is 3-7 months based on published natural history studies and the data from our P20-NS080199 study. The subjects will be stratified into two groups for the analysis: 1) subjects randomized based on EEG biomarkers <12months, 2) subjects randomized based on EEG biomarker >12 months of age. There will be 2 additional groups in the analysis: subjects with normal EEGs, seizure free and never randomized and subjects with electrographic seizures at baseline, never randomized but treated with vigabatrin (the 28-30 children not randomized). Additional analysis will be done to measure the impact of concomitant AEDs used during the study.

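### Read literally, an exploratory Cox analysis of time to first clinical seizure takes epilepsy type and treatment response, known only after a seizure, as covariates

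*Combined protocol and SAP*

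**What the plan says.** The sentence is in the combined protocol and SAP, section Analyses, in the paragraph on EEG biomarker feasibility. It opens "Exploratory analysis will further evaluate the timing of EEG change with time to seizure onset and type of EEG change" and goes on, after the word with, to "epilepsy type and treatment response as a covariate in the Cox proportional hazards assessment of time to clinical seizure".

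Three other places in Analyses bear on how to read it:

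- The opening paragraph sets the main test of the seizure effect, the proportion seizure free: "This will be assessed at two years of follow-up using a chi square test and an intention to treat analysis".
- The same paragraph gives the Cox model of treatment a supporting role ("Supportive analyses will use a time to first seizure analysis using Cox regression methods to evaluate the treatment effects") and lists its terms: "Cox models with age, gender, baseline number of epileptiform discharges included with treatment group will be attempted".
- The paragraph on additional measures, referring back to what was noted above, says "Cox regression models will be attempted with the pre-treatment covariates from the baseline and index EEG". It explains these as the biomarker findings that led to randomisation.

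Secondary objective 1 starts the clock for time to first clinical seizure at randomisation.

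**The concern.** A Cox model for time from randomisation to first seizure can validly use what is known at randomisation. Epilepsy type is not known then; a child acquires one only when seizures occur. Response to seizure treatment comes later still. If treatment response meant response to the blinded study drug, it would be seizure freedom, which is the outcome itself.

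Children who never seize have no value on these variables. Either they are dropped as missing, or they form a category with no events. In the second case the category separates the data completely, and the partial likelihood reduces to the children who did seize. Both routes condition on the outcome. The model then describes how early seizures came among children who had one, and says nothing about whether seizures occurred.

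What is at stake is the exploratory part of secondary objective 4, the feasibility of EEG biomarkers. A hazard ratio for type of EEG change from this model could be reported as evidence for or against the biomarker when it is neither. Any treatment term in the same model would have the same defect.

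**Working it through.** **Inputs** (Statistical Methods, Primary Study Objective, sample-size paragraphs): 24 children per arm; seizure proportion 22/24 = 0.917 on placebo; 5/24 = 0.208 on vigabatrin, with 10/24 = 0.417 as the less favourable case.

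**Plan's own figures.** The disputed sentence gives no hazard ratio, event count or power. The only figures on the same inputs are for a different test, Fisher's exact test, for which the plan states: "exact test with a 0.05 two-sided significance level will have 99% power to detect the difference". Exact enumeration gives 0.9998 at 0.917 versus 0.208, and 0.963 at 22/24 versus 10/24, where the plan states more than 90%. Both stated figures hold. They serve here only to confirm the inputs.

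**Children left in the comparison.**

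| Vigabatrin rate | With a seizure | Vigabatrin lost | Placebo lost |
|---|---|---|---|
| 5/24 | 22 + 5 = 27 of 48 | 24 - 5 = 19 | 24 - 22 = 2 |
| 10/24 | 22 + 10 = 32 of 48 | 24 - 10 = 14 | 24 - 22 = 2 |

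Those lost are mostly the vigabatrin children in whom seizures were prevented.

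**Effect on the treatment hazard ratio.** The documents give no seizure-time distribution for a Cox model, so two assumptions were simulated.

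*Exponential times over a common follow-up.* The hazard ratio implied by the planning rates is ln(1 - p_vigabatrin) / ln(1 - p_placebo):

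- ln(0.792) / ln(0.083) = 0.094
- ln(0.583) / ln(0.083) = 0.217

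*Uniform times, the same in both arms, among children who seize.* The plan mentions uniform seizure timing, but only to project time on vigabatrin (Analyses, paragraph on the medication possession ratio).

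Median treatment hazard ratios (1,500 simulated trials per scenario for exponential timing, 800 for uniform; seizure-only fits needed at least 2 vigabatrin events):

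| Timing | Vigabatrin rate | All children, treatment only | Seizure-only children |
|---|---|---|---|
| Exponential | 0.208 | 0.09 | 0.57 |
| Exponential | 0.417 | 0.21 | 0.61 |
| Uniform | 0.208 | 0.11 | 1.06 |
| Uniform | 0.417 | 0.26 | 0.99 |

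Under exponential timing the literal model was also fitted, with epilepsy type and response entered and never-seized children coded as having no epilepsy. It gave 0.55 and 0.58. That run assumed that half of seizures are spasms, a refractory share of 5/24 (from the pilot's 19 well-controlled and 5 refractory children), and type and response independent of arm.

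**Why the two timings differ.** Among children who seized, uniform timing makes the arms identical, so a ratio near 1 follows by construction. Under exponential timing the higher placebo hazard brings placebo seizures earlier, so some difference remains. Neither number estimates the effect on seizure risk.

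**Check on the remedy.** Replacing the post-seizure variables by a covariate known at randomisation (simulated as non-prognostic, 50% prevalence, exponential timing) gives 0.09 and 0.21, the same as treatment alone.

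**The case against.** The strongest reply is that the sentence need not mean this. Covariate is in the singular, and the sentence has two parallel pairings: EEG timing with seizure timing, and EEG type with epilepsy type and response. On that reading the EEG change is the covariate, and epilepsy type and response are only things to which it is related. The later paragraph on additional measures points back to earlier text and names pre-treatment EEG covariates, which favours this benign reading. The sentence is labelled exploratory, and drug-resistant epilepsy, one form of treatment response, is already an outcome compared between groups by Fisher's exact test.

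Most of this stands, and it limits the point to one sentence. It does not remove it. Of three grammatical readings (EEG change as the covariate, treatment response alone, or both post-seizure variables), two put a post-seizure variable into the model. The later paragraph does not withdraw them.

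Three stronger inferences are tempting but unsupported:

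- *That the trial's treatment effect would be erased.* The main seizure test is the chi-square comparison, and the supportive Cox model lists age, gender, baseline discharges and treatment group. Neither uses these variables. A hazard ratio near 1 in the affected model also depends on uniform timing.
- *That the stated 99% power is lost.* That figure belongs to Fisher's exact test on all randomised children, which this sentence does not touch.
- *That the concomitant-AED analysis has the same fault.* The plan says only "Additional analysis will be done to measure the impact of concomitant AEDs used during the study". It names no Cox model and no covariate role, so no such error can be attributed to it.

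**Conclusion.** The point holds for one exploratory sentence on its literal reading. A Cox model of time to first seizure that includes epilepsy type or treatment response conditions on its own outcome, and neither its EEG-type nor its treatment hazard ratio can be interpreted. On the planning rates about 27 of 48 children would carry the comparison. In simulation the treatment hazard ratio moves from about 0.09-0.26 to between about 0.55 and 1.

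The count rests only on the plan's seizure proportions. The hazard-ratio range rests also on assumed seizure timing, which the documents do not give for this analysis, and at its lower end on the assumed mix of epilepsy types and responses. The direction does not depend on these choices: in every case the ratio moves most of the way towards 1 because children without seizures no longer contribute.

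The trial's main conclusion about seizures is not at risk. The authors may well have intended the valid model; the text should say so before unblinding.

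**What to change.** Reword the sentence in the EEG biomarker feasibility paragraph along these lines:

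> Exploratory Cox models of time from randomisation to first clinical seizure will include only covariates known at randomisation: age at (or timing of) the index EEG change and type of epileptiform abnormality on the index EEG. Epilepsy type and treatment response will not be covariates in these models. They will be summarised descriptively, by arm and by type of index EEG change, among children who have had a seizure.

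This matches the paragraph on additional measures. The summaries among children with seizures should be labelled as not being randomised comparisons. If a formal link between index EEG type and epilepsy type is wanted, first seizures of each type can be analysed as competing events over all randomised children.

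The cost is a change to the SAP wording. No new data, visits or participants are needed.

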**EXCLUSION CRITERIA:**

- 1) Is greater than 6 months of age
- 2) Has not been diagnosed with TSC
- 3) History of seizures or infantile spasms, or evidence of subclinical electrographic seizures on a previous video EEG
- 4) Has received any anticonvulsant medication including vigabatrin, other anti-seizure therapeutic agent including cannabidiol
- 5) Has received an oral mTOR inhibitor such as everolimus or sirolimus
- 6) Has taken an investigational drug, including but not limited to cannabidiol, as part of a research study 30 days prior to enrollment, or plans on taking an investigational drug at any time during the duration of the study
- 7) Is currently enrolled, or plans on enrolling at any time during the duration of the study, in an experimental behavioral early intervention study
- 8) Has a history of being born prematurely (born less than <30 weeks gestation at the time of delivery)

Subjects who have consented and at the time of their baseline study visit and show evidence of electrographic seizures on their initial video EEG will exit from the PREVeNT study and proceed with initiation of management of their clinical condition. All other enrolled subjects will be followed until the age of 36 months with physical and neurologic exams, serial 1-hour awake and sleep video-EEGs, and ophthalmologic evaluation at baseline and defined intervals, every 6-12 weeks based on subjects chronological age.

Study visits and procedures are based on subjects' chronological age in months ( $\pm$ 1 week if under 12 months of age and  $\pm$ 2 weeks if 12 months and older). Once enrolled, subjects enter a 'watchful waiting' protocol which includes baseline EEG at 1.5 month (~6 week) intervals until 12 months of age, then every 3 month (~12 week) intervals until 24 months of age. Subjects will continue in this protocol phase until treatment is justified.

Randomization will be stratified into two groups, according to age at time of emergence of EEG biomarkers: 1)  $\leq$  7 months; 2)  $>$ 7 months of age. This is to account for natural history studies and data from our P20-NS080199 study that indicates mean age of clinical seizure onset less than 7 months of age, with a significant portion of TSC infants developing seizures between 6-12 months and still others after 12 months of age. Accordingly, this randomization strategy will ensure we are able to evaluate age independently of timing of EEG change and treatment randomization.

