For the accurate identification of clinical seizures, parents and caregivers will review a seizure recognition video at the time of study enrollment and retain it as a reference throughout the study. They will also be encouraged to video any suspicious events during the study period for review by clinicians of the investigation team. If at any point during the study the subject is suspected of having a clinical seizure, the parents/caregiver will be instructed to contact their site's study coordinator. The subject will be seen as soon as possible for a study visit and a video EEG will be completed for confirmation of clinical or electrographic seizure onset. Those subjects with either a documented clinical seizure on video or evidence of an electrographic seizure on video EEG will be transitioned to the Open-Label treatment phase.

At the emergence of abnormal epileptiform activity (*i.e.* sharp waves, spikes or polyspikes, spike and wave discharges, classic or modified hypsarrhythmia) prior to the onset of the first clinical or electrographic seizure, subjects will enter the protocol blinded-treatment phase (Arm A). Emergence of these specific, predetermined EEG biomarkers detected by video EEG will lead to a 1:1 randomization with vigabatrin or placebo. The vigabatrin and placebo will be dispensed as a sachet and those subjects randomized to vigabatrin will be titrated up to 100mg/kg/day by 50mg/kg/day every 3 days during the blinded phase of the study. The research pharmacist at each site will be unblinded during this phase of the study and the vigabatrin and placebo sachets doses will be identical in order to maintain the blind.

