- *Randomizes the participant:* Participants who are candidates for this trial will be recruited using well established protocols to identify these participants. Inclusion and exclusion criteria forms will be completed prior to randomization to ensure eligibility. Informed consent and/or assent for participation will be carried out by the participant or legally authorized representative in circumstances where the potential participant is not competent to do so. Participants will be randomized using the web-based integrated data management system. Usually a permuted block randomization scheme will be employed, with stratification by clinical site and block sizes of 2, 4, and 6 (assuming 2 groups). Nevertheless, the coordinator will enter critical elements of eligibility to ensure the identification of the participant and the eligibility of the participant. After the entry of these data, the coordinator will be asked to confirm that the participant is to be irrevocably randomized, and, after confirmation, the treatment PID2 will be provided.
- *Assists in the management of participant flow in the center:* After randomization, the system updates the schedule for treatment, tests and assessments for the rest of the hospital stay or clinic visit, and future follow up contacts. The scheduling portion of the system provides real-time reports of expected treatments to be delivered and visits and participant encounters for the clinic or on the telephone. In addition, the system prints participant-specific forms for each encounter, ensuring that the correct forms (and only the correct forms) are completed.
- *Tracks drug supplies:* The system records the use of the drug in the inventory system that is jointly maintained by the DCC, trial Central Pharmacy, and the site pharmacies. The Central Pharmacy will also have access to portions of the web-based system to review and monitor the drug inventory at each site, and regular reports are produced, showing drug inventory levels and identifying sites requiring resupply.

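### The 7-month randomisation stratum is missing from the Bayley-III and chi-square analyses, the supplementary analysis groups are cut at 12 months instead, and the randomisation scheme is described in two ways

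*Combined protocol and SAP*

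**What the plan says.** Four parts of the combined protocol and SAP bear on this.

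- **Protocol description, after the exclusion criteria.** "Randomization will be stratified into two groups, according to age at time of emergence of EEG biomarkers", with the groups being 7 months or younger and older than 7 months. The stated purpose is that "this randomization strategy will ensure we are able to evaluate age independently of timing of EEG change and treatment randomization". Site is not mentioned. Allocation is equal: biomarker emergence "will lead to a 1:1 randomization with vigabatrin or placebo".
- **Data and Monitoring Plan, item on randomising the participant.** "Usually a permuted block randomization scheme will be employed, with stratification by clinical site and block sizes of 2, 4, and 6". Age is not mentioned.
- **Additional measures and analyses considerations.** Randomised children are grouped for analysis as "subjects randomized based on EEG biomarkers <12months, 2) subjects randomized based on EEG biomarker >12 months of age". No model is attached to this grouping. It stands beside two further groups of children who were never randomised.
- **Analyses.** The Bayley-III cognitive score is analysed with a constrained longitudinal model "which assumes a common mean across treatment groups at Baseline and a different mean for each treatment at each of the post-Baseline time points", with time as a categorical variable. No age stratum or site term is named. For the proportion seizure free, "This will be assessed at two years of follow-up using a chi square test and an intention to treat analysis", again with no stratum. In support, "Cox models with age, gender, baseline number of epileptiform discharges included with treatment group will be attempted".

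**The concern.** A factor used to stratify the randomisation would normally appear in the primary analysis. Stratification makes the arms more alike on that factor than chance would. If the factor also predicts the outcome, an analysis that ignores it counts between-stratum variation as noise. The standard error is then too large, the test rejects too seldom under the null, and power is lost.

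Here the age factor is used in the design but not in the Bayley-III model or the chi-square test. The only age grouping named for analysis uses a different cut-point. The text also does not settle whether age, site or both define the randomisation strata. If this stays open until unblinding, the choice of adjustment and of age cut could be made with the results in view. The planned power is 85% for a large effect (0.885 SD), so a few points are worth having when they cost almost nothing.

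**Working it through.** **1. The plan's own figures.** These come from the sample-size text: 24 per arm, effect size 0.885, two-sided 0.05. The noncentral t distribution with 46 degrees of freedom gives 85.1%, against the stated 85%. For seizures, Fisher's exact test at 0.917 versus 0.208 gives 99.98% (stated 99%). At 0.917 versus 0.417 it gives 96.3% (stated as above 90%). All three reproduce. They assume no stratification, so they are a baseline and do not test the point.

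**2. Size of the randomisation cells.** There are 15 sites and about 48 randomised children. Site alone gives 48/15 = 3.2 per site. Site by age gives 48/(15 × 2) = 1.6 per cell, so blocks of 2, 4 and 6 would rarely fill. Simulated mean imbalance between arms within an age stratum is 0.7 children with age-only blocks, about 3.1 with site-only blocks and about 2.8 with site-by-age blocks. Which scheme was used therefore matters for age balance.

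**3. Cost of omitting the stratum, by formula.** Assumptions not in the documents: 40% of randomised children are in the older stratum, and the strata differ by δ total SDs on the Bayley-III. The between-stratum share of variance is 0.4 × 0.6 × δ², and the within-stratum SD is σ = √(1 − 0.24δ²). With age balanced by design (normal approximation):

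- type I error, unadjusted: 2[1 − Φ(1.96/σ)]
- power, unadjusted: Φ[(0.885√12 − 1.96)/σ]
- power, adjusted: Φ[0.885√12/σ − 1.96]

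Here √12 = √(24/2) and 0.885√12 = 3.066.

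| δ | σ | Type I error, unadjusted | Power, unadjusted | Power, adjusted | Gain (points) |
|---|---|---|---|---|---|
| 0 | 1.000 | 5.0% | 86.6% | 86.6% | 0 |
| 0.5 | √0.94 = 0.970 | 4.3% | 87.3% | 88.5% | 1.2 |
| 0.8 | √0.8464 = 0.920 | 3.3% | 88.5% | 91.5% | 3.0 |

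The normal approximation runs a little over 1 point high (86.6% against 85.1% at δ = 0).

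**4. The same cost by simulation** (48 children, blocks of 2, 4 and 6, 40% older, 15 sites).

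- Age-stratified blocks, δ = 0.8: type I error is about 3.4% without the stratum and about 5% with it. Power is 87% and 90%.
- δ = 0.5: adjustment gains 1 to 2 points. δ = 0: it gains nothing.
- Site-only or site-by-age blocks, δ = 0.8: the unadjusted test stays near its nominal level (about 4.6% to 4.7%). Adjustment for age still gains about 4 to 5 points.

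**5. Does the 12-month cut substitute?** A separate simulation of 6,000 trials per setting assumed half the children in each 7-month stratum and 15% above 12 months. The stratum explained 10%, 20% or 30% of the variance. With equal strata this is a difference of 2√R², or 0.63, 0.89 and 1.10 SD.

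| Variance explained | Type I error: none / 12-month / 7-month | Power: none / 12-month / 7-month |
|---|---|---|
| 0% | 4.8 / 4.9 / 4.9% | 86 / 85 / 85% |
| 10% | 4.3 / 4.4 / 5.3% | 86 / 86 / 89% |
| 20% | 3.0 / 3.7 / 5.4% | 88 / 87 / 92% |
| 30% | 2.3 / 3.1 / 5.4% | 88 / 88 / 95% |

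Monte Carlo error is about √(0.85 × 0.15/6000) = 0.5 points for power and √(0.05 × 0.95/6000) = 0.3 points for type I error. The 12-month term recovers almost nothing in this setting. The simulated outcome steps at 7 months, however, so the comparison favours that cut by construction.

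**The case against.** Much can be said for the plan, and most of it stands.

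- **Site stratification.** The item is worded as what is usual. It also mentions assent and a hospital stay, which fit an outpatient infant trial poorly. It reads as generic data-centre text and does not exclude age. A reader might infer that site replaced age; the documents do not show that. Nor do they establish that the age scheme was the one implemented.
- **Prognosis.** A reader might infer that the protocol stratifies because age at EEG change predicts the Bayley-III score. It does not say so. Its reasons concern age at seizure onset and separating age from treatment. The background links early-onset epilepsy with developmental problems, which is only indirect support.
- **The 12-month groups.** It is tempting to say that the randomisation does not protect comparisons within them. Age at biomarker emergence is fixed before allocation, so those comparisons remain randomised. Only designed balance is missing. The cut also has some basis: the EEG interval lengthens at 12 months, and the protocol mentions seizure onset after 12 months. The grouping is supplementary, and leaving exactly 12 months unassigned is a wording slip, though 12 months is a scheduled EEG visit.
- **Seizure analyses.** Age is already in the supportive Cox models, and the chi-square comparison has ample power under the plan's assumptions. Little is at stake there.
- **The calculations** use simple linear models, not the planned longitudinal model. A baseline cognitive score could absorb part of an age effect. Whether one will exist is unclear: the schedule footnotes give only the social-emotional and adaptive questionnaire at 6 months, with the Bayley-III itself from 12 months.

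What remains is that no section reconciles these statements, and the Bayley-III model and the chi-square test as written omit the stratum.

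**Conclusion.** The point holds as a mismatch between design and analysis that is cheap to repair. The conflict in the text is certain; its cost is conditional. If the 7-month strata differ by 0.5 SD on the Bayley-III, omitting the stratum costs about 1 to 2 points of power. At 0.8 SD it costs about 3 to 5 points, and the test runs at about 3.4% if blocks were stratified by age. If age does not predict the score, nothing is lost, and adjustment costs almost nothing. The stratum difference, the 40% older share and equal site sizes are assumptions; the documents give none of them.

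A reader might infer a biased treatment estimate or an inflated type I error. Neither follows: the error is on the conservative side, and the planned sample size and 85% power stand.

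**What to change.** Settle the following in the SAP before unblinding.

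1. Add the 7-month age stratum as a fixed effect in the Bayley-III longitudinal model, with its interaction with time if wanted.
2. For consistency, use the same stratum in the seizure analyses: a Cochran-Mantel-Haenszel test for the proportion seizure free, and a stratified log-rank test or Cox model for time to first seizure.
3. Make the protocol description and the Data and Monitoring Plan state the one randomisation scheme actually implemented, checked against the randomisation system.
4. Under the additional analyses, use the 7-month groups. Alternatively, keep the 12-month split as a labelled exploratory subgroup, with exactly 12 months assigned to one side.

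The cost is wording and one degree of freedom in the Bayley-III model (more if the time interaction is added). No new data are needed, because age at biomarker emergence is known for every randomised child. If blocks turn out to have been by site, the age term is still a valid pre-randomisation covariate.
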